5.3.2. Per Protocol Population

Participants in the FAS population who are considered to be sufficiently compliant with the Protocol compose the PP population, which is defined for supportive sensitivity analyses for primary efficacy endpoint in the double-blind period. Participants with important protocol deviations, as defined in Section 6.3, will be excluded from the PP population.

5.3.3. Safety Population

All randomized participants who applied ruxolitinib cream or vehicle cream at least once will constitute the safety population. Treatment groups for this population will be determined according to the actual treatment the participant applied on Day 1 regardless of assigned study treatment.

All safety analyses will be conducted using the safety population.

5.3.4. Treatment-Extension Evaluable Population

Participants who applied at least 1 application of ruxolitinib cream in treatment extension period will constitute the TE evaluable population.

5.3.5. Pharmacokinetic/Pharmacodynamic Evaluable Population

The PK/PD evaluable population will include all participants who applied ruxolitinib cream at least once and provided at least 1 postdose plasma sample (1 PK/PD measurement) that complies with the instruction in the Protocol. Participants in whom it is not possible to obtain a blood sample for PK/PD from an area of the body that was not treated with (exposed to) study drug (eg, due to difficulties of technical/ procedural nature) will not be included in the PK/PD evaluable population because of the material risk of the contamination of such a sample with study drug from the skin through which a needle is passed. The study pharmacokineticist will review data listings of study drug application and sample records to identify participants to be excluded from PK data analyses. The study research investigator will review data listings of PD data and sample records to identify participants to be excluded from analyses of PD data.

6. BASELINE, EXPOSURE, AND DISPOSITION VARIABLES AND ANALYSES

[Appendix A](#) provides a list of planned tables, figures, and listings. Sample data displays are included in a separate document.

6.1. Baseline and Demographics, Physical Characteristics, and Disease History

6.1.1. Demographics

The following demographics will be summarized for the FAS and Safety population during the DB period and the TE evaluable population in the TE period: age, age group, sex, race, ethnicity, region, weight, height, and BMI.

6.1.2. Baseline Disease Characteristics

Baseline disease characteristics summarized for the FAS and Safety population include but are not limited to the following:

- Time since initial diagnosis of vitiligo
- Vitiligo diagnosed in childhood (No/Yes [age]: 0-5 years, 6-11 years, 12-17 years)
- Disease status (stable/progressive)
- Skin type (type I/II/III/IV/V/VI)
- Other autoimmune disorders
- Prior therapy given for vitiligo (predefined systemic treatments, phototherapy, and surgical procedures)
- History of acne vulgaris (No/Yes)

- Currently have acne vulgaris on the face (No/Yes)
- Vitiligo in genital area (No/Yes)
- Baseline F-VASI
- Baseline T-VASI
- Baseline F-BSA involvement (% of the total body)
- Baseline T-BSA involvement (% of the total body)

6.1.3. Prior Therapy for Vitiligo

Prior medication information for vitiligo will be used to identify other non-predefined medication received by participants before enrollment into the study. Prior medications for vitiligo will be summarized by treatment group.

6.1.4. Medical History

For participants in the safety population during the DB period, medical history will be summarized by assigned treatment group. This summary will include the number and percentage of participants with medical history for each body SOC/PT as documented in the eCRF.

6.2. Disposition of Participants

The number and percentage of participants who were randomized, treated, and completed the DB period and of participants who discontinued the treatment or withdrew from the study during the DB period with a primary reason for discontinuation will be summarized for both the FAS and safety population during the DB period.

The number and percentage of participants who completed the TE period and discontinued treatment or withdrew from the study during the TE period with a primary reason for discontinuation will be summarized for the TE evaluable population in the TE period.

6.3. Protocol Deviations

In general, the following are important protocol deviations that may significantly affect the primary and gated secondary analyses:

- Missing primary endpoint on F-VASI;
- Compliance < 60% based on the application numbers.

Participants with 1 or more such deviations will be excluded from the PP population. In addition, protocol deviations related to inclusion/exclusion criteria, discontinuation criteria, and use of excluded concomitant medications will be reviewed. Decisions as to whether any of these deviations warrant exclusion from the PP population will be made before breaking the blind.

6.4. Exposure

For participants in the safety population during the DB period and participants in the TE evaluable population during the TE period, descriptive statistics will be provided by treatment group for duration of treatment, average daily dose, and total dose. Summary for overall

exposure including DB and TE periods will be provided for participants continually using 1.5% BID. Duration of treatment with ruxolitinib cream or vehicle cream is defined as the number of days from Day 1 to the last record of ruxolitinib cream or vehicle cream application in the specific period.

6.5. Study Drug Compliance

Overall compliance (%) for the application of ruxolitinib cream or vehicle cream during the DB and treatment extension periods will be calculated for all participants in the safety population as follows:

$$\text{Overall application compliance (\%)} = 100 \times [\text{total number of nonmissing applications}] / [\text{total number of intended applications}]$$

where the total number of nonmissing applications is the total number of applications that the participant actually applied in each period during the study. The total number of intended applications is the number of planned applications minus the number of interrupted applications.

6.6. Prior and Concomitant Medication

For participants in the safety population during the DB period, prior medications and concomitant medications will be coded using the WHO Drug Dictionary and summarized as number and percentage of participants with prior and concomitant medications by WHO drug class and WHO drug term. For participants in the treatment extension period (ie, the TE evaluable population), only concomitant medications will be summarized.

Prior and concomitant medications will be summarized by treatment group as well as listed.

7. EFFICACY

[Appendix A](#) provides a list of planned tables, figures, and listings. Sample data displays are included in a separate document.

7.1. General Considerations

For all continuous variables, both the actual value and change and/or percentage from baseline (if available) will be analyzed.

All by-visit analyses will include the follow-up period if the data are available.

7.2. Efficacy Measures

7.2.1. Body Surface Area

Total % BSA (includes facial and nonfacial areas) depigmented by vitiligo will be estimated at each visit. Body surface area assessment will be performed by the Palmar Method. Body surface area should be estimated to the nearest 0.1%. The approximate size of the participant's entire palmar surface (ie, the palm plus 5 digits) should be considered as 1% BSA, and the approximate size of the participant's thumb should be considered as 0.1% BSA.

7.2.2. Vitiligo Area Scoring Index

Areas affected by depigmentation due to vitiligo will be assessed using the VASI. It is based on a composite estimate of the overall area of vitiligo patches at baseline and the degree of macular repigmentation within these patches over time.

Facial VASI (F-VASI) is measured by percentage of vitiligo involvement (% of BSA) and the degree of depigmentation. The percentage of BSA (hand unit) vitiligo involvement is estimated by the investigator using the Palmar Method. Hand unit is based on participant's hand size. Investigator uses his/her hand to mimic the participant's hand size to evaluate percentage of BSA vitiligo involvement. The degree of depigmentation for each vitiligo involvement site is determined and estimated to the nearest of the following percentages: 0, 10%, 25%, 50%, 75%, 90%, or 100%. At 100% depigmentation, no pigment is present; at 90%, specks of pigment are present; at 75%, the depigmented area exceeds the pigmented area; at 50%, the depigmented and pigmented area are equal; at 25%, the pigmented area exceeds the depigmented area; at 10%, only specks of depigmentation are present. The F-VASI is then derived by multiplying the values assessed for the vitiligo involvement by the percentage of affected skin for each site on the face and summing the values of all sites together (possible range 0-3).

Total body VASI (T-VASI) is calculated using a formula that includes contributions from all body regions (possible range, 0-100).

$$VASI = \sum_{\text{all body sites}} [\text{hand units}] \times [\text{Residual Depigmentation}]$$

The body is divided into the following 6 separate and mutually exclusive sites: 1) head/neck, 2) hands, 3) upper extremities (excluding hands), 4) trunk, 5) lower extremities (excluding feet), and 6) feet. The percentage of vitiligo involvement is estimated in hand units (% of BSA) by the same investigator during the entire course of the study. Hand unit is based on participant's hand size. The investigator uses his/her hand to mimic the participant's hand size to evaluate % BSA vitiligo involvement. The degree of depigmentation for each body site is determined and estimated to the nearest of the following percentages: 0%, 10%, 25%, 50%, 75%, 90%, or 100%. The T-VASI is then derived by multiplying the values assessed for the vitiligo involvement by the percentage of affected skin for each body site and summing the values of all body sites together ([Hamzavi et al 2004](#)).

The categorical variable F-VASI25 will be equal to 1 for percentage improvement from baseline in F-VASI of $\geq 25\%$ and will be equal to 0 for percentage improvement of $< 25\%$. F-VASI50/75/90 and T-VASI25/50/75/90 are defined with the same pattern.

7.2.3. Physician's Global Vitiligo Assessment (Facial)

The severity of vitiligo will be assessed by the physician using the PhGVA, which has a 5-point scale ([Table 3](#)). Response will be reported for face (F-PhGVA).

Table 3: Facial Physician's Global Vitiligo Assessment Scale

Score	Severity	Description
0	Clear	No signs of vitiligo or complete/near complete repigmentation
1	Almost Clear	Mostly pigmented areas with small depigmented or difficult to repigment areas (eg, philtrum, nares, corners of eyes, perioral skin)
2	Mild Disease	Modest areas of depigmentation (not more than half of facial skin) with approximately 50% pigmentation within vitiligo areas or significant perifollicular pattern present
3	Moderate Disease	Large areas of depigmented vitiligo areas (more than half of facial skin); significant depigmentation within vitiligo areas
4	Severe Disease	Extensive areas of vitiligo to complete depigmentation on face

An F-PhGVA of clear (0) or almost clear (1) can be interpreted as F-PhGVA response.

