5.1. Inclusion Criteria

Participants are eligible to be included in the study only if all of the following criteria apply:

1. Adolescents and adults aged \geq 12 years.
2. Participants with a clinical diagnosis of non-segmental vitiligo with depigmented area including $\geq 0.5\%$ BSA on the face, ≥ 0.5 F-VASI, $\geq 3\%$ BSA on nonfacial areas, ≥ 3 T-VASI, and total body vitiligo area (facial and nonfacial) not exceeding 10% BSA.
3. Participants who agree to discontinue all agents used to treat vitiligo from screening through the final safety follow-up visit. Over-the-counter preparations deemed acceptable by the investigator and camouflage makeups are permitted.
4. Male and female participants must be willing to take appropriate contraceptive measures to avoid pregnancy or fathering a child for the duration of study participation with the exception of the following:
 - a. Females of non-childbearing potential (ie, or surgically sterile with a hysterectomy and/or bilateral oophorectomy OR postmenopausal, ≥ 12 months of amenorrhea without an alternative medical cause).
 - b. Prepubescent adolescents.

Note: Information about specific types of acceptable contraceptive measures and duration of contraceptive use are provided in [Appendix A](#).

5. For adult participant, ability to comprehend and willingness to sign an ICF; for adolescent participant, written informed consent of the parent(s) or legal guardian and written assent from the adolescent participant.

Note: Adolescents, who during the course of the study become legal adults, will be asked for their consent to continue the study, and in the event of lack thereof, will be discontinued from further participation.

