8.2.4. Physician's Global Vitiligo Assessment (Total Body)

The severity of total body vitiligo will be assessed by the physician using the PhGVA, which has a 5-point scale ([Table 12](#)). Response will be reported for total body (T-PhGVA).

Table 12: Total Body Physician's Global Vitiligo Assessment Scale

Score	Severity	Description
0	Clear	No signs of vitiligo or complete/near complete repigmentation
1	Almost Clear	Mostly pigmented areas with small depigmented or difficult to repigment areas (eg, hands, feet, philtrum, nares, corners of eyes, perioral skin)
2	Mild Disease	Modest areas of depigmentation with approximately 50% pigmentation within vitiligo areas or significant perifollicular pattern present
3	Moderate Disease	Large areas of depigmented vitiligo areas; significant depigmentation within vitiligo areas
4	Severe Disease	Extensive areas of vitiligo with complete depigmentation

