To further assess the efficacy of ruxolitinib cream.	
 • Proportion of participants achieving an F-PhGVA of clear (0) or almost clear (1) during the treatment period (double-blind and treatment extension periods). • Proportion of participants achieving a T-PhGVA of clear (0) or almost clear (1) during the treatment period (double-blind and treatment extension periods). • Proportion of participants in each F-PhGVA category during the treatment period (double-blind and treatment extension periods). • Proportion of participants in each T-PhGVA category during the treatment period (double-blind and treatment extension periods). • Proportion of participants who report F-PaGIC-V of very much improved or much improved during the treatment period (double-blind and treatment extension periods). • Proportion of participants in each F-PaGIC-V category during the treatment period (double-blind and treatment extension periods). • Proportion of participants who report T-PaGIC-V of very much improved or much improved during the treatment period (double-blind and treatment extension periods). • Proportion of participants in each T-PaGIC-V category during the treatment period (double-blind and treatment extension periods). • Proportion of participant in each category for the color-matching question during the treatment period (double-blind and treatment extension periods).
To determine the participants' quality of life.	
 • Change from baseline in WHO-5 during the treatment period (double-blind and treatment extension periods). • Actual measurements in TSQM during the treatment period (double-blind and treatment extension periods). • Change from baseline in VitiQoL during the treatment period (double-blind and treatment extension periods). • Change from baseline in HADS during the treatment period (double-blind and treatment extension periods).
To evaluate translational biomarkers in the blood of participants treated with ruxolitinib cream.	
 • Change from baseline in the expression of select biomarkers in peripheral blood at Weeks 12, 24, 40, and 52.

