7.2.4. Physician's Global Vitiligo Assessment (Total Body)

The severity of total body vitiligo will be assessed by the physician using the PhGVA, which has a 5-point scale ([Table 4](#)). Response will be reported for total body (T-PhGVA).

Table 4: Total Body Physician's Global Vitiligo Assessment Scale

Score	Severity	Description
0	Clear	No signs of vitiligo or complete/near complete repigmentation
1	Almost Clear	Mostly pigmented areas with small depigmented or difficult to repigment areas (eg, hands, feet, philtrum, nares, corners of eyes, perioral skin)
2	Mild Disease	Modest areas of depigmentation with approximately 50% pigmentation within vitiligo areas or significant perifollicular pattern present
3	Moderate Disease	Large areas of depigmented vitiligo areas; significant depigmentation within vitiligo areas
4	Severe Disease	Extensive areas of vitiligo with complete depigmentation

An T-PhGVA of clear (0) or almost clear (1) can be interpreted as T-PhGVA response.

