7.6. Analysis of Exploratory Efficacy Parameters

7.6.1. Exploratory Efficacy Analysis

Similar to the secondary efficacy endpoints, all exploratory efficacy analyses will be conducted based on the FAS population during the treatment period (double-blind and treatment extension periods).

Mean, change (if applicable) from baseline, and percentage change (if applicable) from baseline will be summarized by treatment and visit using descriptive statistics for the following:

- WHO-5 Total Score
- TSQM Subscales (Effectiveness, Convenience, Overall satisfaction)
- VitiQoL Total scales and Subscales
- HADS Anxiety and Depression scores

Categorical endpoints at postbaseline visits will be summarized by treatment and visit using descriptive statistics, including the following:

- F-PhGVA and T-PhGVA
- F-PaGIC-V and T-PaGIC-V
- Color-matching question

- Proportion of participants achieving T-PhGVA response
- Proportion of participants achieving F-PhGVA response
- Proportion of participants achieving F-PaGIC-V response
- Proportion of participants achieving T-PaGIC-V response

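### PhGVA response is scored from the visit value alone, so a participant graded almost clear on Day 1 would count as a responder without improving (exploratory endpoints; low priority)

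*SAP*

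**What the plan says.** SAP 7.2.3 states for the face: "An F-PhGVA of clear (0) or almost clear (1) can be interpreted as F-PhGVA response". SAP 7.2.4 states for the total body: "An T-PhGVA of clear (0) or almost clear (1) can be interpreted as T-PhGVA response". The endpoint list in SAP 2.2 adds no baseline condition: "Proportion of participants achieving an F-PhGVA of clear (0) or almost clear (1) during the treatment period (double-blind and treatment extension periods". It places both PhGVA responses in the exploratory tier, outside the fixed testing sequence of SAP 3.2.

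The inclusion criteria (Protocol 5.1) set floors on area and on VASI. For the face these include "BSA on the face, ≥ 0.5 F-VASI", with at least 0.5% BSA. For the body they include at least 3% nonfacial BSA and "≥ 3 T-VASI, and total body vitiligo area (facial and nonfacial) not exceeding 10% BSA". No inclusion or exclusion criterion refers to PhGVA.

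Protocol Table 3 schedules both PhGVA scores on Day 1 and at Weeks 12 and 24, so a baseline value exists. SAP 7.6.1 does not use it: "Categorical endpoints at postbaseline visits will be summarized by treatment and visit using descriptive statistics". SAP 6.1.2 lists baseline F-VASI, T-VASI, F-BSA and T-BSA, but not PhGVA.

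**The concern.** A response rate is normally read as the share of participants who got better. Here it is the share found at 0 or 1, including any who were already there on Day 1. Tables 2.5.1 and 2.6.1 and Figures 4.6 and 4.7 are titled as achieving, or proportions achieving, that state, so the reader is invited to see improvement.

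PhGVA is the exception among the plan's response proportions. VASI response is a percentage improvement from baseline (SAP 7.2.2). VNS asks for a comparison with the time before treatment (SAP 7.2.5.1). PaGIC-V asks about change since treatment began (SAP 7.2.5.3 and 7.2.5.4). At stake is how readable two exploratory endpoints are: their rates could be too high in both arms, and the contrast between arms diluted.

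**Working it through.** The plan states no PhGVA rate, power or sample size, so there is no figure to reproduce. The check has two parts.

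**1. Can an eligible participant be graded 1 on Day 1?**

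Take 0.5% BSA of perioral skin and 3.5% BSA on hands and feet, all fully depigmented (residual depigmentation 100%).

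| Criterion (Protocol 5.1) | Value | Met? |
|---|---|---|
| Facial BSA ≥ 0.5% | 0.5% | yes |
| F-VASI ≥ 0.5 | 0.5 × 1.00 = 0.5 | yes |
| Nonfacial BSA ≥ 3% | 3.5% | yes |
| T-VASI ≥ 3 | (0.5 + 3.5) × 1.00 = 4.0 | yes |
| Total BSA ≤ 10% | 4.0% | yes |

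Now compare this participant with the total body grades (Protocol Table 12, repeated in SAP Table 4):

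- Grade 1 is "Mostly pigmented areas with small depigmented or difficult to repigment areas (eg, hands, feet, philtrum, nares, corners of eyes, perioral skin". All the involved skin lies at sites that this grade names.
- Grade 2 needs roughly half the pigment back within the lesions, or a marked perifollicular pattern. Fully depigmented skin has neither.
- Grade 3 needs large areas with substantial depigmentation inside them. A rater could choose this grade, since for the body it has no half-of-skin threshold.

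Grade 1 is therefore plausible, though not forced. More generally, "total body vitiligo area (facial and nonfacial) not exceeding 10% BSA" leaves at least 90% of the body uninvolved in every participant.

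The facial case is weaker. F-VASI runs from 0 to 3, so the floor of 0.5 is 0.5/3 = 16.7% of the maximum. A fully depigmented area of that size does not match facial grade 2 (about half pigmented within lesions, or perifollicular pattern) or facial grade 3 (more than half of facial skin). That gap leaves the choice to the rater.

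**2. What would it do to the reported rates?**

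Let b be the share of each arm that enters at 0 or 1 and stays there, and p the response rate among those who enter at 2 or more. Then:

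- reported rate = b + (1 − b)p
- reported difference = (1 − b)(p_active − p_vehicle)

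Assume p = 20% and 5%, the same pair that SAP Table 2 uses for F-VASI75, taken here only for illustration. With about 300 participants at 2:1 (200 and 100):

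| b | Active | Vehicle | Difference (points) | Odds ratio | Fisher power (2-sided 0.05) |
|---|---|---|---|---|---|
| 0% | 20.0% | 5.0% | 15.0 | 4.75 | 0.97 |
| 5% | 24.0% | 9.8% | 14.2 | 2.92 | 0.86 |
| 10% | 28.0% | 14.5% | 13.5 | 2.29 | 0.75 |
| 20% | 36.0% | 24.0% | 12.0 | 1.78 | 0.54 |

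For b = 10%: 0.10 + 0.90 × 0.20 = 0.280 and 0.10 + 0.90 × 0.05 = 0.145; the difference is 0.90 × 15.0 = 13.5 points.

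The power column matters only if a comparison is run. SAP 7.6.1 plans description, but Protocol 10.3.1.3 allows logistic models where applicable, and Tables 2.5.1 and 2.6.1 are titled as both summary and analysis.

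Restricting to Day 1 scores of 2 or more returns the b = 0 rates on fewer participants. At b = 10% that is 180 and 90 instead of 200 and 100.

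**The case against.** The strongest reply is that grade 1 may not mean what the example needs. The neighbouring grades describe pigment within lesions: near-complete repigmentation at 0, about half at 2, substantial loss at 3. Read in that sequence, grade 1 means lesions that have mostly repigmented, and an untreated, fully depigmented patch would not qualify. If the phrase about mostly pigmented areas referred to the whole body, the 10% cap would make it true of everyone and it would separate no one. In addition, 3.5% BSA is three and a half palmar surfaces under the plan's own measure, which a rater may not call small.

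This stands as a reason for caution about how often grade 1 would be given on Day 1. It does not close the gap. The scale text supports both readings, the plan does not say which raters are to use, and the response definition has no baseline condition to protect it.

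A second reply is that the endpoint describes attaining a state, while change is already covered by VASI and PaGIC-V. That is fair, and it is a reason to keep the all-participant rate rather than replace it.

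A third is that the endpoints are exploratory and no alpha depends on them. That is correct, and it sets the priority.

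**Conclusion.** The definition permits response without improvement, and the entry limits do not prevent it. Both arms' rates would be raised and the risk difference multiplied by (1 − b). The size is unknown because the documents give no baseline PhGVA distribution. The illustrative 28.0% against 14.5% at b = 10% rests on assumed true rates of 20% and 5%, on equal baseline shares in the two arms (which randomisation should give on average), and on those participants staying at 0 or 1.

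Some stronger conclusions that a reader might infer are not supported:

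- **False superiority, or a threat to the main results.** Baseline scores should balance across randomised arms, so the expected effect is dilution. Primary and key secondary endpoints do not use PhGVA.
- **Baseline scores hidden from the reader.** The SAP 6.1.2 list is expressly not exhaustive, and Listings 2.6.6 and 2.6.7 cover individual F-PhGVA and T-PhGVA scores. A baseline summary is simply not guaranteed.
- **A known number of affected participants, or a tolerance that is exceeded.** The documents supply neither.
- **Lack of a confirmatory visit as a fault of PhGVA.** The primary endpoint is also scored at a single visit.

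This is a cheap improvement of low priority.

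**What to change.** In SAP 7.2.3, 7.2.4 and 7.6.1, and so in Tables 2.5.1 and 2.6.1 and Figures 4.6 and 4.7, report PhGVA response (0 or 1 at the visit) among FAS participants whose Day 1 score was 2 or more. Keep the all-FAS rate alongside, labelled as the proportion in that state at the visit. Name baseline F-PhGVA and T-PhGVA in SAP 6.1.2, so that the share entering at 0 or 1 is reported by arm. A further row requiring at least a 2-grade fall from baseline is optional.

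The cost is SAP wording and one added row or series in two exploratory tables and two figures. No new data are needed, because PhGVA is already scored on Day 1. The restriction uses a pre-treatment value, so the comparison between randomised arms is preserved. The only downside is a slightly smaller denominator in the restricted row.
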